Clinical outcomes	
 Proportion of progression free survival/time to progression (at intervals per standard of care). Proportion of objective response rate (at intervals per standard of care). Complete response defined as complete reduction of all visible disease; partial response defined as partial reduction in size of visible disease in some or all areas without any areas of increase in visible disease; stable disease defined as no change in overall size of visible disease, also including cases where some lesions increased in size and some lesions decreased in size; progressive disease defined as an increase in visible disease and/or presence of any new lesions, including cases where the clinician indicates progressive disease. Time to response (at intervals per standard of care), defined as the time to first response among patients who achieved complete response or partial response. Proportion of overall survival (1- and 2-years post-treatment initiation). 	Patient records

Variable	Operational Definition	Data Source(s)
All lab investigations + other investigations	
 All lab investigation conducted including complete blood count (CBC). 	Patient records
Quality of life	
 To be assessed via EORTC QLQ-C30 (Cancer Quality of Life Questionnaire). 	Patient questionnaire

BC = breast cancer; CBC = complete blood count; ECOG = Eastern Cooperative Oncology Group; EORTC QLQ-C30 = European Organization for the Research and Treatment of Cancer Quality of Life Questionnaire Core 30; MBC = metastatic breast cancer.

Table 2. Data Entry Schedule

Data Collection and Entry ¹ ►	Baseline	During Treatment with Palbociclib	Post Treatment with Palbociclib
	SOC Visit ¹	SOC Follow-up visits ² through End of Treatment with Palbociclib	SOC Follow-up Visits through End of Study ³
Informed Consent & Inclusion/Exclusion Criteria	x		
Patient Demographics, Medical History, Baseline Metastatic Disease Status	x		
BC Diagnosis and Recurrence History	x		
Comorbid conditions	x	x	
Concomitant Medications	x	x	
BC Treatment ⁴	x	x	x ⁵
Performance Status (ECOG)	x	x	
Clinical Outcomes ⁶	x	x	
Laboratory investigations, including CBC ⁷	x	x	
EORTC QLQ-C30 ⁸	x	x	

BC = breast cancer; SOC = standard of care; CBC = complete blood count; ECOG = Eastern Cooperative Oncology Group; EORTC QLQ-C30 = European Organization for the Research and Treatment of Cancer Quality of Life Questionnaire Core 30.

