1. Data is collected in accordance with normal standard of care visits; enter all data available per Data Entry Schedule into the electronic data capture system.
2. For a visit to be considered a follow-up visit, clinical outcomes data must be collected at minimum, in accordance with SOC.
3. Follow-up through End of Study: Enter data at SOC visits post palbociclib treatment.
4. BC treatment: including surgery, radiation, systemic chemotherapy, hormone therapy, and/or targeted therapy, in both neoadjuvant/adjuvant and metastatic disease settings, prior to, during and after palbociclib treatment; supportive care is also collected in the metastatic setting.
5. Data on the first immediate subsequent treatment used after the end of palbociclib treatment should be collected.
6. Clinical outcomes: overall clinical response as judged by treating physician, at intervals per standard of care schedule: progression free survival/time to progression, objective response rate, time to response and overall survival.
7. CBC: Baseline and during palbociclib treatment, enter any CBC during the 1st 3 cycles, then enter Day 1 (or prior to start of a new cycle) CBC for the subsequent cycles as per standard of care.
8. EORTC QLQ-C30 will be collected at baseline (before starting palbociclib) then every 3 months \pm 2 weeks after initiating treatment with palbociclib for the first year of treatment. After the first year of treatment with palbociclib, EORTC QLQ-C30 will be collected every 6 months \pm 4 weeks until the end of treatment with palbociclib.

PFIZER CONFIDENTIAL

CT24-WI-GL02-RF01 3.0 Non-Interventional Study Protocol Template For Primary Data Collection Study

02-Nov-2020

Page 19 of 41

090177e19bc3ff14\Approved\Approved On: 10-Nov-2022 09:28 (GMT)

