3. ANALYSIS SETS/POPULATIONS

3.1. Full Analysis Set

The Full Analysis Set will contain all patients who fulfil the eligibility criteria. Date of enrollment is the date of Palbociclib treatment initiation (baseline).

Censoring rules: The maximum follow-up of a patient is 24 months. Patients will be censored at the end of Palbociclib treatment, or if the treatment continues, at 24 months. Other censoring events before 24 months are patient's withdrawal, disease progression or death, whichever occurs first. Patients' subsequent treatments after Palbociclib treatment discontinuation /disease progression will be recorded. Patients who are lost to follow-up will be censored at their last visit. For some clinical outcomes, different censoring rules will be applied as described in [Section 6.1](#), [Section 6.2](#), and [Section 6.3](#).

Data collection is estimated to start in Q2 2021 and it will end in Q4 2024.

Table and Figure Shells are presented in [ANNEX 2](#).

Patient inclusion and exclusion criteria are explained in [Section 2.1](#). Summary of patient enrolment per country and study site will be described as shown in [Table Shell 1](#).

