6.1. Analysis for the Primary Objectives

Patients enrollment per country and site will be summarized as shown in [Table Shell 1](#).

For the primary objectives, clinical outcomes including the proportion of progression free and alive patients at different time intervals (6, 12, 18 and 24 months) and the proportion of patients who are alive 1 and 2 years post Palbociclib treatment initiation will be reported as shown in [Table Shell 2](#). The stratified tables will be presented as in Table Shells [3](#) - [9](#). The stratifications will be performed as described in [Section 3.2](#) by at least combination therapy and line of therapy.

The progression of the disease will be considered whenever the overall tumor response reported at any follow-up visit is progressive disease. The Kaplan-Meier (KM) method (product-limit method) will be used to estimate the proportion of subjects who are progression-free. The KM-estimate will be presented by 6 month intervals (6, 12, 18 and

24 months since the beginning of Palbociclib treatment) including the number of patients who were progression-free, those still at risk and the proportion of progression-free patients.

The proportion of the patients who are alive 1 and 2 years after Palbociclib treatment initiation will be calculated as the ratio of the number of patients who are alive 1 and 2 years over the number of patients who started the treatment (eligible patients).

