6.3. Analysis for the Exploratory Objectives

For the exploratory analyses, time to response (TTR), time to progression (TTP)/ progression free survival (PFS) will be studied and results will be presented as shown in [Table Shell 54](#). The stratified tables will be presented as in Table Shells [55-61](#).

TTR is defined as the length of time (in days) from the initiation of Palbociclib treatment until the first reported disease response (complete or partial).³⁴ Censoring rules presented in [Section 3.1](#) will be applied.

TTP is defined as the length of time (in days) from the initiation of Palbociclib treatment until the first reported disease progression.³⁴ Patients will be censored at the end of Palbociclib treatment, death, time of withdrawal, or end of the 24-month follow-up, whichever occurs first, at the respective time point. Specifically, death is not included in TTP but is considered as censoring event.

PFS is defined as the length of time (in days) from the initiation of Palbociclib treatment until the first reported disease progression or death due to any cause, whichever occurs first.³⁴ The disease progression will be considered at the first follow-up visit after the Palbociclib treatment initiation when the overall tumor response recorded is progressive disease. Patients with no disease progression documented will be censored at the last available medical record entry or end of the follow-up period. Patients who are lost to follow-up will be censored at their last visit.

Survival analyses will be used to estimate time to event endpoints TTR, TTP and PFS. The results of the survival analysis will be presented as the Kaplan-Meier survival curves and their 95% confidence intervals (CIs) that will be calculated using the log-log transformation of the survival probabilities.³⁶ Together with the Kaplan-Meier plots, the number of patients at risk at time intervals (eg, 90 days or as seen appropriate for the study) will be reported. [Figure Shells 1 and 2](#) show how time to response (TTR) and progression free survival (PFS) will be visualized as Kaplan-Meier plots including the number of patients at different time intervals. Kaplan-Meier plots can be presented by other categories (see [Section 3.2](#)), if enough data are available. Moreover, the results of the survival analysis will be reported as a descriptive summary table including the number of patients at risk, the number of patients

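### Exploratory PFS is censored at the last record entry although tumour outcomes are scheduled only during palbociclib; where records outlast tumour assessment, PFS is biased upwards

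*SAP*

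**What the plan says.** **PFS event.** SAP 6.3 defines PFS as time to progression or death from any cause. Progression comes from the tumour response: "The disease progression will be considered at the first follow-up visit after the Palbociclib treatment initiation when the overall tumor response recorded is progressive disease".

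**PFS censoring.** "Patients with no disease progression documented will be censored at the last available medical record entry or end of the follow-up period". The text does not say which of the two dates applies if they differ, and it does not refer to a tumour assessment. Patients lost to follow-up are censored at their last visit.

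**TTP censoring, one paragraph earlier.** "Patients will be censored at the end of Palbociclib treatment, death, time of withdrawal, or end of the 24-month follow-up, whichever occurs first".

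**General rule, SAP 3.1.** "Patients will be censored at the end of Palbociclib treatment, or if the treatment continues, at 24 months". The same section allows exceptions, "For some clinical outcomes, different censoring rules will be applied as described in" Sections 6.1, 6.2 and 6.3.

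**Schedule.** In Protocol Table 2 (Section 8.3) the row "Clinical Outcomes ⁶" is marked at baseline and during palbociclib, and its post-treatment cell is empty. SAP Table 1 is the same. The only row marked after treatment is breast cancer treatment, for the first subsequent therapy.

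**Length of follow-up.** Protocol 8.1 and 8.2 follow patients for 24 months, including after palbociclib. SAP 2.1 ends follow-up at the end of palbociclib, progression or withdrawal. The variable for reason of end of follow-up in SAP Annex 1 lists death, withdrawal, loss to follow-up and completion of 24 months, but not the end of palbociclib.

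**The concern.** A Kaplan-Meier estimate is sound only if patients in the risk set could have had an event recorded. SAP Annex 1 lists toxicity, patient decision and poor adherence among the reasons for stopping palbociclib, so some patients will stop before progressing. If the chart stays active but no further tumour response is entered, the PFS rule keeps them at risk while a progression could not be seen. They enlarge the denominator without being able to contribute a progression, and the curve is too high.

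TTP in the same section is censored at the end of palbociclib and does not have this feature. TTP and PFS would therefore differ because of their censoring dates as well as because PFS counts deaths. SAP 6.1 gives the primary progression-free proportions no censoring rule of their own, so the SAP 3.1 default applies. The report could then show two inconsistent progression-free estimates from the same patients.

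**Working it through.** The plan has no figure that depends on this rule, so there is nothing to reproduce. The documents give no rate of stopping without progression, so the rates below are assumptions.

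**Inputs (assumed).** Exponential PFS with median 20 months, so λ = ln 2/20 = 0.03466 per month. Stopping without progression at d = 0.01 or 0.02 per month, independent of prognosis; 1 − exp(−12d) gives 11% or 21% stopped by month 12. No tumour response is recorded after stopping.

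**True value at 24 months.** exp(−24λ) = 43.5%.

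**Case A: records run to month 24, no later event captured.**
On treatment and event-free: u(t) = exp(−(λ+d)t). Stopped and still counted event-free: w(t) = d/(λ+d) × (1 − u(t)). The rule estimates u + w.
- d = 0.01: 0.342 + 0.2239 × 0.658 = 0.490, overstated by 5.4 points.
- d = 0.02: 0.269 + 0.3659 × 0.731 = 0.537, overstated by 10.1 points.

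**Case B: records run to month 24, deaths captured.** A stopped patient progresses unseen at rate λ and then dies at rate μ = ln 2/18 or ln 2/36 (assumed post-progression median of 18 or 36 months). The probability of being alive x months after stopping is S(x) = (μe^(−λx) − λe^(−μx))/(μ − λ). The estimate is u(24) + ∫ d·u(s)·S(24 − s) ds.
- d = 0.01: 47.4% to 48.1%, overstated by 3.9 to 4.6 points.
- d = 0.02: 50.8% to 52.0%, overstated by 7.2 to 8.5 points.

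Simulation of this case gives 3.8 to 8.5.

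**Case C: last record three months after stopping.** After month 3 the apparent hazard is λ/[1 + d/(λ+d) × (e^(3(λ+d)) − 1)].
- d = 0.01: 0.2239 × 0.1434 = 0.032, so 0.969λ. Over 24 months this acts like 2.95 + 21 × 0.969 = 23.3 months of true hazard; PFS 44.6%, overstated by 1.1 points.
- d = 0.02: 0.3659 × 0.1782 = 0.065, so 0.939λ, or 2.91 + 21 × 0.939 = 22.6 months; PFS 45.7%, overstated by 2.1 points.

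Simulation allowing for deaths in those three months gives 0.9 to 2.1.

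| 24-month PFS, true value 43.5% | Overstatement (points) |
|---|---|
| C: records end 3 months after stopping | 0.9 to 2.1 |
| B: records to month 24, deaths captured | 3.8 to 8.5 |
| A: records to month 24, nothing captured | 5.4 to 10.1 |

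**Effect on the reported median.** Table Shell 54 reports the median and quartiles. Simulations used medians quoted in Protocol 6.1, with an assumed 5-30% stopping without progression by month 12. With a true median of 9.5 months and records to month 24, the estimated median is 9.7 to 11.8 months. With a true median of 20.2 months it is 21.1 to 23.0 months at 5-10% stopping and is not reached by month 24 at 20-30%. If records end three months after stopping, the 20.2-month median becomes about 20.4 to 22.1. The direction was upward in every scenario.

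**The case against.** **Follow-up may end with palbociclib.** If the end of follow-up is read with SAP 2.1, and as the earlier of the two dates, censoring falls at the end of palbociclib and the bias largely disappears. This is a possible reading. It conflicts with Protocol 8.1 and 8.2 and with the reasons for end of follow-up in SAP Annex 1. It also sits badly beside TTP, which is given an explicit end-of-palbociclib rule that PFS lacks.

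**Tumour data may be collected off treatment.** A reader might infer that the schedule definitely stops progression ascertainment. The documents do not support that. Footnote 6 places overall survival in the same row, so a literal reading would stop death capture too, although survival at 1 and 2 years is a primary objective. Protocol 8.2 collects data after treatment, schedule footnote 3 asks for data entry at post-palbociclib visits, and footnote 2 says: "For a visit to be considered a follow-up visit, clinical outcomes data must be collected at minimum, in accordance with SOC". But footnote 2 is attached to the on-treatment column, and the post-treatment cell stays empty. Capture is unclear, and could vary by site.

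**Records may not run to month 24.** Laboratory tests and concomitant medications are also unmarked after treatment; the only marked item is the first subsequent therapy. Case C may therefore be nearer than A or B.

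**The primary result.** A reader might infer that the primary proportions carry this bias. They use the same event source, "The progression of the disease will be considered whenever the overall tumor response reported at any follow-up visit is progressive disease", but the last-record sentence belongs to exploratory PFS, and SAP 6.1 falls under the SAP 3.1 default.

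**Deaths.** A reader might infer that the sentence censors deaths without documented progression. The PFS definition just before it, and SAP Annex 1, make death an event. Only the loose wording, and an event label in Table Shell 54 that names progression alone, leave room for doubt.

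**Conclusion.** The concern stands as a conditional one. Where records continue after palbociclib and tumour response is not recorded, the SAP 6.3 rule biases exploratory PFS upwards. The documents contradict each other on whether that will occur, and the SAP should settle it before analysis.

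Under the assumptions above, the 24-month overstatement is about 1 to 2 points if records end three months after stopping and about 4 to 8.5 points if they run to month 24 with deaths captured. The 5.4 to 10.1 points of Case A are a worst case, since death is a PFS event and the end-of-study form records it. All these sizes rest on assumed stopping rates and on stopping that is unrelated to prognosis. An effect on the primary proportions is not shown. The study is descriptive, so no test or sample size is affected; the consequence is a distorted published estimate.

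**What to change.** Replace the PFS censoring sentence in SAP 6.3 by:

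> Patients without documented progression or death are censored at the date of their last recorded overall tumour response (day 1 if there is no post-baseline assessment). Death without documented progression is an event if it occurs within a prespecified interval after the last tumour assessment; otherwise the patient is censored at that assessment.

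This works whether or not tumour responses are entered off treatment, because any that are entered count. The interval is needed: if every later death counted while survivors were censored at their last assessment, 24-month PFS would be understated by about 0.6 to 2.2 points in simulation under the same assumptions.

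In addition:
- Reconcile the follow-up definitions in SAP 2.1 and 3.1 with Protocol 8.1 and 8.2, and state whether tumour response is entered after palbociclib.
- State in SAP 6.1 that the primary progression-free proportions use the same rule. If this is a major change to the primary analysis, Protocol 8.7 calls for a protocol amendment.
- Correct the PFS event label in Table Shell 54 to include death.
- Keep the last-record rule, and the counting of all deaths, as sensitivity analyses.

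The cost is mainly SAP text, possibly an amendment, fewer patients at risk at late time points and slightly wider intervals. The new rule also assumes that stopping without progression is non-informative, which the report should say.

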7. LIST OF TABLE AND FIGURE SHELLS

Table 2. List of Table and Figure Shells

Objective	Number	Description
Primary objectives 1, 2, Secondary objective 1	Table Shell 1	Summary of patients enrollment per country and site
	Table Shell 2	Descriptive summary table of clinical outcomes of Palbociclib treatment.
	Table Shell 3	Descriptive summary table of clinical outcomes of Palbociclib treatment by combination of therapies.
	Table Shell 4	Descriptive summary table of clinical outcomes of Palbociclib treatment by line of endocrine therapy.
	Table Shell 5	Descriptive summary table of clinical outcomes of Palbociclib treatment by country.
	Table Shell 6	Descriptive summary table of clinical outcomes of Palbociclib treatment by menopausal status.
	Table Shell 7	Descriptive summary table of clinical outcomes of Palbociclib treatment by metastatic status.
	Table Shell 8	Descriptive summary table of clinical outcomes of Palbociclib treatment by metastatic site.
	Table Shell 9	Descriptive summary table of clinical outcomes of Palbociclib treatment by age group.
Secondary objective 2	Figure Shell 1	Kaplan Meier plot to describe progression free survival by type of combination therapy.
	Table Shell 10	Descriptive summary table of the demographic and initial clinical profiles of BC patients who have received Palbociclib treatment as first line therapy for metastatic/locally advanced BC.
	Table Shell 11	Descriptive summary table of the demographic and initial clinical profiles of BC patients who have received Palbociclib treatment as second line therapy for metastatic/locally advanced BC.
	Table Shell 12	Descriptive summary table of the clinical profiles of BC patients at the initiation of Palbociclib treatment as first line therapy for metastatic/locally advanced BC.
Secondary objective 3	Table Shell 13	Descriptive summary table of the clinical profiles of BC patients at the initiation of Palbociclib treatment as second line therapy for metastatic/locally advanced BC.
	Table Shell 14	Descriptive summary table of Palbociclib treatment characteristics.
	Table Shell 14	Descriptive summary table of Palbociclib treatment

PFIZER CONFIDENTIAL

Objective	Number	Description
Secondary objective 4		characteristics by combination of therapies.
	Table Shell 15	Descriptive summary table of Palbociclib treatment characteristics by line of endocrine therapy.
	Table Shell 16	Descriptive summary table of Palbociclib treatment characteristics by country.
	Table Shell 17	Descriptive summary table of Palbociclib treatment characteristics by menopausal status.
	Table Shell 18	Descriptive summary table of Palbociclib treatment characteristics by metastatic status at the initiation of Palbociclib treatment.
	Table Shell 19	Descriptive summary table of Palbociclib treatment characteristics by metastatic site at the initiation of Palbociclib treatment.
	Table Shell 20	Descriptive summary table of Palbociclib treatment characteristics by age group at the initiation of Palbociclib treatment.
	Table Shell 21	Descriptive summary table of the supportive therapies received by the patients during the Palbociclib treatment.
	Table Shell 22	Descriptive summary table of the supportive therapies received by the patients during the Palbociclib treatment by combination of treatments.
	Table Shell 23	Descriptive summary table of the supportive therapies received by the patients during the Palbociclib treatment by line of therapy.
	Table Shell 24	Descriptive summary table of the supportive therapies received by the patients during the Palbociclib treatment by country.
	Table Shell 25	Descriptive summary table of the supportive therapies received by the patients during the Palbociclib treatment by menopausal status.
Secondary objective 5	Table Shell 26	Descriptive summary table of the supportive therapies received by the patients during the Palbociclib treatment by metastatic status.
	Table Shell 27	Descriptive summary table of the supportive therapies received by the patients during the Palbociclib treatment by metastatic site.
	Table Shell 28	Descriptive summary table of the supportive therapies received by the patients during the Palbociclib treatment by age group.
	Table Shell 29	Descriptive summary table of therapies for the treatment of early or locally advanced BC (stages 0-IIIa) who have received Palbociclib treatment at any point of time in the BC treatment.
	Table Shell 30	Descriptive summary table of the therapies by combination therapy for the treatment of early or locally advanced BC (stages 0-IIIa) who have received Palbociclib treatment at any point of time in the BC treatment.

PFIZER CONFIDENTIAL

CT24-WI-GL03-RF02 2.0 *Non-Interventional Statistical Analysis Plan For Primary Data Collection Study 01-*
Jun-2020

Objective	Number	Description
Secondary objective 6	Table Shell 31	Descriptive summary table of the therapies by line of endocrine therapy for the treatment of early or locally advanced BC (stages 0-IIIa) who have received Palbociclib treatment at any point of time in the BC treatment.
	Table Shell 32	Descriptive summary table of the therapies by country for the treatment of early or locally advanced BC (stages 0-IIIa) who have received Palbociclib treatment at any point of time in the BC treatment
	Table Shell 33	Descriptive summary table of the therapies by menopausal status for the treatment of early or locally advanced BC (stages 0-IIIa) who have received Palbociclib treatment at any point of time in the BC treatment.
	Table Shell 34	Descriptive summary table of the therapies by metastatic status for the treatment of early or locally advanced BC (stages 0-IIIa) who have received Palbociclib treatment at any point of time in the BC treatment.
	Table Shell 35	Descriptive summary table of the therapies by metastatic site for the treatment of early or locally advanced BC (stages 0-IIIa) who have received Palbociclib treatment at any point of time in the BC treatment.
	Table Shell 36	Descriptive summary table of the therapies by age group for the treatment of early or locally advanced BC (stages 0-IIIa) who have received Palbociclib treatment at any point of time in the BC treatment.
	Table Shell 37	Descriptive summary table of therapies of the advanced/metastatic BC patients (stages IIIb-IV) before Palbociclib treatment.
	Table Shell 38	Descriptive summary table of therapies of the advanced/metastatic BC patients (stages IIIb-IV) by combination of therapies before Palbociclib treatment.
	Table Shell 39	Descriptive summary table of therapies of the advanced/metastatic BC patients (stages IIIb-IV) by line of endocrine therapy before Palbociclib treatment.
	Table Shell 40	Descriptive summary table of therapies of the advanced/metastatic BC patients (stages IIIb-IV) by country before Palbociclib treatment.
	Table Shell 41	Descriptive summary table of therapies of the advanced/metastatic BC patients (stages IIIb-IV) by menopausal status before Palbociclib treatment.
	Table Shell 42	Descriptive summary table of therapies of the advanced/metastatic BC patients (stages IIIb-IV) by metastatic status before Palbociclib treatment.
	Table Shell 43	Descriptive summary table of therapies of the advanced/metastatic BC patients (stages IIIb-IV) by metastatic site before Palbociclib treatment.
	Table Shell 44	Descriptive summary table of therapies of the advanced/metastatic BC patients (stages IIIb-IV) by age group before Palbociclib treatment.

PFIZER CONFIDENTIAL

CT24-WI-GL03-RF02 2.0 *Non-Interventional Statistical Analysis Plan For Primary Data Collection Study 01-*
Jun-2020

Objective	Number	Description
Secondary objective 7	Table Shell 45	Descriptive summary table of quality of life of the patients receiving Palbociclib combination treatment.
	Table Shell 46.1	Descriptive summary table of quality of life of the patients receiving Palbociclib combination treatment by combination. Palbociclib plus letrozole/aromatase inhibitor.
	Table Shell 46.2	Descriptive summary table of quality of life of the patients receiving Palbociclib combination treatment by combination. Palbociclib plus fulvestrant.
	Table Shell 47.1	Descriptive summary table of quality of life of the patients receiving Palbociclib combination treatment by line of treatment. First line.
	Table Shell 47.2	Descriptive summary table of quality of life of the patients receiving Palbociclib combination treatment by line of treatment. Second line.
	Table Shell 48.1	Descriptive summary table of quality of life of the patients receiving Palbociclib combination treatment by country. Egypt.
	Table Shell 48.2	Descriptive summary table of quality of life of the patients receiving Palbociclib combination treatment by country. Jordan.
	Table Shell 48.3	Descriptive summary table of quality of life of the patients receiving Palbociclib combination treatment by country. Lebanon.
	Table Shell 48.4	Descriptive summary table of quality of life of the patients receiving Palbociclib combination treatment by country. Kingdom of Saudi Arabia.
	Table Shell 48.5	Descriptive summary table of quality of life of the patients receiving Palbociclib combination treatment by country. Qatar.
	Table Shell 48.6	Descriptive summary table of quality of life of the patients receiving Palbociclib combination treatment by country. Morocco.
	Table Shell 48.7	Descriptive summary table of quality of life of the patients receiving Palbociclib combination treatment by country. United Arab Emirates.
	Table Shell 49.1	Descriptive summary table of quality of life of the patients receiving Palbociclib combination treatment by menopausal status. Premenopausal.
	Table Shell 49.2	Descriptive summary table of quality of life of the patients receiving Palbociclib combination treatment by menopausal status. Postmenopausal.
	Table Shell 50.1	Descriptive summary table of quality of life of the patients receiving Palbociclib combination treatment by metastatic status. De novo.
	Table Shell 50.2	Descriptive summary table of quality of life of the patients receiving Palbociclib combination treatment by metastatic status. Recurrent.

PFIZER CONFIDENTIAL

Objective	Number	Description
	Table Shell 51.1	Descriptive summary table of quality of life of the patients receiving Palbociclib combination treatment by metastatic site. Visceral.
	Table Shell 52.1	Descriptive summary table of quality of life of the patients receiving Palbociclib combination treatment by metastatic site. Non-visceral.
	Table Shell 53.1	Descriptive summary table of quality of life of the patients receiving Palbociclib combination treatment by age group. (Age is defined at the treatment initiation). Age group <55 years.
	Table Shell 53.2	Descriptive summary table of quality of life of the patients receiving Palbociclib combination treatment by age group. (Age is defined at the treatment initiation). Age group 55-64 years.
	Table Shell 53.3	Descriptive summary table of quality of life of the patients receiving Palbociclib combination treatment by age group. (Age is defined at the treatment initiation). Age group ≥65 years.
	Table Shell 54	Descriptive summary table of the time to response, progression and progression free survival in Palbociclib treatment patients.
	Table Shell 55	Descriptive summary table of the time to response, progression and progression free survival in Palbociclib treatment patients by treatment combination.
	Table Shell 56	Descriptive summary table of the time to response, progression and progression free survival in Palbociclib treatment patients by line of therapy.
	Table Shell 57	Descriptive summary table of the time to response, progression and progression free survival in Palbociclib treatment patients by country.
	Table Shell 58	Descriptive summary table of the time to response, progression and progression free survival in Palbociclib treatment patients by menopausal status.
	Table Shell 59	Descriptive summary table of the time to response, progression and progression free survival in Palbociclib treatment patients by metastatic status.
Exploratory objective 1	Table Shell 60	Descriptive summary table of the time to response, progression and progression free survival in Palbociclib treatment patients by metastatic site.
	Table Shell 61	Descriptive summary table of the time to response, progression and progression free survival in Palbociclib treatment patients by age group.
	Figure Shell 2	Kaplan Meier plot to describe time to response by type of combination therapy.
Exploratory objective 2	Table Shell 62	Descriptive summary table of the first immediate subsequent treatment used following end of treatment with Palbociclib.

PFIZER CONFIDENTIAL

CT24-WI-GL03-RF02 2.0 *Non-Interventional Statistical Analysis Plan For Primary Data Collection Study 01-*
Jun-2020

Page 23 of 172

0901776099673e30A540de5dFampalh5read On: 28-Feb-2023 09:56 (GMT)

090177e1990673e39a54dc25f1a9a15read On: 28-Feb-2023 09:56 (GMT)

